As this is a feasibility/pilot study, data from the study will be used to estimate effect sizes and inform a larger, randomized trial on the effects of the SinuSonic on individuals with compromised autonomic regulation, if warranted by the results.

Background: The SinuSonic was developed as a non-pharmaceutical device aimed to reduce nasal congestion via simultaneous administration of acoustic vibration and gentle oscillating expiratory pressure. Previous studies have demonstrated significant improvements in congestion and ease of breathing after immediate use of the device (Cairns & Bogan, 2019) and after twice daily use for 5-weeks (Soler et al., 2020). In this study, there was significant improvement in peak nasal inspiratory flow after only 2 weeks of use, and significant improvement in multiple self-report measures of congestion after 5 weeks of use. No adverse effects were reported. A review report by Schlosser, Salley and Soler likewise concluded that the device may improve pregnancy-related rhinitis, which may be particularly important for individuals who would prefer non-pharmacological interventions while pregnant or breastfeeding (<https://sinusonic.com/blogs/learn/pregnancy-rhinitis.>)

[figure not shown]
There are common clinical symptoms, such as anxiety and depression, that are frequently associated in individuals who feel unhealthy. The Polyvagal Theory (Porges, 1995, 1998, 2001, 2003, 2007) provides a model for which these psychological and physical symptoms may be viewed as the predictable consequences of a common neural substrate. This neural substrate involves the neural regulation of the heart and lungs, as well as neural regulation of the muscles of the face and head which function together as a Ventral Vagal Complex (VVC).

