The Eligibility Screening will consist of the following questions:

- 1) Are you between ages 18-99 years old? [YES TO QUALIFY]
- 2) Have you ever used the SinuSonic device? [NO TO QUALIFY]
- 3) Do you meet any of the conditions listed under the Safety and Warnings for use of the SinuSonic device? [NO TO QUALIFY]
 - a) Current or history of breathing problems (i.e., asthma, chronic obstructive pulmonary disorder (COPD), chronic bronchitis, emphysema, pneumonia, pleural effusion, lung cancer, cancer of the throat or upper airway)

- b) Current or history of circulatory problems (i.e., active nose bleed, heart arrhythmia, coronary artery disease, congestive heart failure, heart attack)
- c) Other conditions, specified as brain tumor, moderate to severe ear pain, fever greater than 101 degrees

- 4) Have you experienced symptoms of nasal congestion that have persisted at least 2 weeks? [YES TO QUALIFY]
- 5) Is your current level of nasal congestion at 5 or higher? (VAS included here) [YES TO QUALIFY]

Step 2: Consent/Linkage File

When all eligibility criteria are met, individuals will be invited to access the Informed Consent document (also provided via RedCap) to read and e-sign. Phone number and email address for the researcher will be provided in the event of questions or request for clarification.

After receiving the e-signed informed consent, researchers will assign a SubjectID number so that the participant can use the SubjectID number when completing all questionnaire assessment sessions using RedCap. Researchers will maintain a database linking SubjectID and name on their password-protected computers that will not be accessible to anyone who is not affiliated with the research.

Step 3: Pre-SinuSonic assessment

Participants will be asked to complete this assessment, via RedCap, prior to beginning use of the SinuSonic. Researchers will provide participants with a link to the assessment (text or email), along with their unique SubjectID number to use. The following instruments will be programmed into RedCap for completion:

Prior to SinuSonic Use (week 0):

- 1) Demographic Information Form
- 2) SF12 to assess overall health ("how you feel and how well you are able to do your usual activities")
- 3) TNSS to assess current nasal symptoms
- 4) BPQ to reflect perception of autonomic regulation
- 5) HADS to assess anxiety and depression
- 6) ATES to assess history of trauma/adverse events

Step 4: SinuSonic Use / Weekly assessments

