After completing the pre-SinuSonic assessment, researchers will inform participants to begin directed use of the SinuSonic (2 minutes per day, 2 times per day). Participants will be asked to confirm SinuSonic use on a weekly questionnaire. Additionally, participants will be asked to complete the following questionnaires approximately 5 minutes after final SinuSonic use for that week. The following instruments will be programmed into RedCap for completion:

Weekly, for 4 weeks (end of week 1, 2, 3, 4).

- 1) TNSS to assess current nasal symptoms
- 2) PGIC to reflect change in activity limitations, symptoms, emotions and overall quality of life

Step 5: Final research assessment

Participants will be asked to confirm use of the SinuSonic on a weekly questionnaire. Additionally, participants will be asked to complete the following questionnaires approximately 5 minutes after final SinuSonic use on the 5th consecutive week. The following instruments will be programmed into RedCap for completion:

End of Study (end of week 5).

- 1) TNSS to assess current nasal symptoms
- 2) PGIC to reflect change in activity limitations, symptoms, emotions and overall quality of life
- 3) BPQ to reflect perception of autonomic regulation
- 4) HADS to assess anxiety and depression

Description of Measures

Body Perception Questionnaire (BPQ) (Cabrera et al., 2018). The Body Perception Questionnaire (BPQ) is a self-report measure of body awareness and autonomic reactivity. Its items are based on the organization of the autonomic nervous system (ANS), a set of neural pathways connecting the brain and body. These pathways send information from the body about the status of organs and tissues (i.e., afferent projections). Some of these incoming signals form a basis for the subjective awareness of the body. The ANS also carries signals that control the functions of these organs and tissues (i.e., efferent projections). These signals can alter the functions of the body, depending on internal and external needs. Only the Autonomic Reactivity subscale will be distributed and used for the current study.

Hospital Anxiety and Depression Scale (HADS) (Zigmond & Snaith, 1983). HADS is a fourteen-item scale with seven items each for anxiety and depression subscales. Scoring for each item ranges from zero to three. A subscale score >8 denotes anxiety or depression.

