Short-Form Health Survey-12 (Ware et al., 1995). The SF-12 is a health-related quality-of-life questionnaire consisting of twelve questions that measure eight health domains to assess physical and mental health. Physical health-related domains include General Health (GH), Physical Functioning (PF), Role Physical (RP), and Body Pain (BP)

Total Nasal Symptom Score. The Total Nasal Symptom Score (TNSS) is the sum of scores for each of nasal congestion, sneezing, nasal itching, and rhinorrhea at each time point, using a four point scale (0–3), where 0 indicates no symptoms, a score of 1 for mild symptoms that are easily tolerable, 2 for awareness of symptoms which are bothersome but tolerable and 3 is reserved for severe symptoms that are hard to tolerate and interfere with daily activity. TNSS is calculated by adding the score for each of the symptoms to a total out of 12.

Adverse Traumatic Experiences Scale (ATES) (Kolacz et al., 2020). This measure asks about childhood adverse experiences, childhood maltreatment, other person maltreatment, life-threatening situations, sudden deaths of close ones, and personal health situations. Respondent-reported prior adverse events

of maltreatment, life-threatening situations, and sudden deaths of close ones are summed to create an adversity score (range: 0–19).

Patient Global Impression of Change (PGIC) (Hurst & Bolten (2004). The self-report measure Patient Global Impression of Change (PGIC) reflects a patient's belief about the efficacy of treatment. PGIC is a 7 point scale depicting a patient's rating of overall improvement. Patients rate their change as "very much improved," "much improved," "minimally improved," "no change," "minimally worse," "much worse," or "very much worse."

Data Analyses

Questionnaire data will be entered by participants into RedCap for researcher access. Researchers will export the data into SPSS for data analyses. All databases will be stored on password protected computers, accessible only to researchers affiliated with the study, and backed up on UNC servers.

As the current proposal is for a feasibility/pilot study, researchers will evaluate the following aims to determine whether a larger, randomized trial is warranted.

Aim 1: Examine associations between nasal congestion, autonomic functioning, adverse events, and mental health indices (depression, anxiety) at baseline. Pearson correlation analyses will be used to evaluate relationships among measures at each timepoint.

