Aim 2: (*These would be the aims for a future, randomized clinical trial, with preliminary testing using data from the current feasibility/pilot study*): Evaluate the effect of the SinuSonic on users with chronic nasal congestion. We will focus on three constructs important to psychological and physical health and hypothesize that:

- A) Nasal congestion will significantly improve when comparing baseline measures to follow-up measures at each week, and will maintain effects at 5 weeks. Repeated measures ANOVA will be used to evaluate mean change in outcome measures across time in PGIC and TNSS.
- B) Autonomic functioning will significantly improve when comparing baseline measures to end of study. Repeated measures ANOVA will be used to evaluate mean change in BPQ across time.
- C) Mental health indices (depression, anxiety) will significantly improve when comparing baseline measures to end of study. Repeated measures ANOVA will be used to evaluate mean change in HADS across time.

Aim 3: (*This would be an aim for a future, randomized clinical trial, with preliminary testing using data from the current feasibility/pilot study*). Evaluate the mediating effect of current/previous adverse experiences on outcome measures at 5 weeks, using regression models.

Aim 4: Calculate effect sizes for each outcome variable, which will be necessary to determine adequate sample size for a future clinical trial. G-Power software will be used to determine sample sizes based on the effect sizes of the current outcome measures.

References

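### Aim 4 sizes a future randomized trial from the effect sizes of a one-group study and states no conversion or allowance for change that a control arm would share

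*Combined protocol and SAP*

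**What the plan says.** Informing the next trial is a stated use of this study. The pilot statement that closes the Purpose section says "data from the study will be used to estimate effect sizes and inform a larger, randomized trial", and the Data Analyses section adds that "researchers will evaluate the following aims to determine whether a larger, randomized trial is warranted". Aim 4 gives the method: "G-Power software will be used to determine sample sizes based on the effect sizes of the current outcome measures". Aim 4 itself speaks only of a future clinical trial, but the two statements above and the notes under Aims 2 and 3 make clear that it is to be randomized.

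The current study recruits 50 adults into one group. Under Step 4, after the baseline questionnaires, "researchers will inform participants to begin directed use of the SinuSonic". No control or sham arm is described. Aim 2 analyses mean change over time by repeated measures ANOVA.

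Three further features bear on how to read that change:

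- Screening item 4 asks: "Have you experienced symptoms of nasal congestion that have persisted at least 2 weeks".
- Screening item 5 asks, on a VAS: "Is your current level of nasal congestion at 5 or higher".
- Under Step 5, participants are to "complete the following questionnaires approximately 5 minutes after final SinuSonic use on the 5th consecutive week".

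The plan gives no effect-size metric, G-Power module, comparator, alpha, power or size for the future trial. It also gives no control-group data, no important between-arm difference and no rule for turning a within-person change into a between-arm effect.

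**The concern.** A randomized trial is sized on the difference in outcome between its arms. One uncontrolled group supplies the change in treated people, which is the device effect plus whatever would have happened anyway. Nothing in these data separates the two.

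The possible sources of shared change differ in which comparator would share them:

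- **Natural resolution.** Two weeks of symptoms are enough for entry, so some congestion may clear by itself. Any comparator would share this.
- **Regression to the mean.** Entry on a VAS of 5 or higher may be followed by a fall. Any comparator would share this too. The mechanism is less direct for BPQ and HADS, on which nobody is selected.
- **Expectancy.** Ratings are unblinded self-report, made about 5 minutes after use. Only a sham would share this, and the comparator is not named.
- **A true acute response to the device.** Controls would not share this.

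PGIC needs separate mention. It is an Aim 2A outcome but has no baseline, so its effect size is not a before-after change at all, although it is equally uncontrolled.

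If shared change is counted as device effect, the next trial is planned for too large a difference and has less power than intended.

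**Working it through.** **Nothing to reproduce.** The plan gives no sample size for the future trial, and its own 50 comes without alpha, power, effect size or SD. What follows is illustration, and every input is assumed.

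**Inputs.** Mean change divided by the SD of change, dz = 0.5; two-sided alpha 0.05; planned power 80%; 1:1 allocation; equal SDs; no dropout; two-sample t-test on change scores (noncentral t). Let f be the share of the treated-arm change that controls also show.

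**Step 1: size the trial as if dz were the between-arm effect.** d = 0.5 needs 64 per arm, total 128, power 0.801.

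**Step 2: allow controls to change.** The true between-arm effect is d = 0.5 × (1 − f).

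| f | true d | power at total 128 | total needed for 80% |
|---|---|---|---|
| 0% | 0.500 | 0.801 | 128 |
| 10% | 0.450 | 0.714 | 158 |
| 25% | 0.375 | 0.558 | 226 |
| 50% | 0.250 | 0.289 | 506 |

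The needed size grows roughly as 1/(1 − f)², which is 1.23, 1.78 and 4.00 for the last three rows. The loss hardly depends on the assumed dz. By the normal approximation, with dz of 0.3, 0.5 or 0.8 and planned power of 80%, true power is about 56% at f = 25% and about 29% at f = 50% in all three cases.

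**Step 3: a separate matter, the metric and the model, with f = 0.** If the same change is divided by the baseline SD, with equal SDs at both times and baseline-to-week-5 correlation r, the value entered is 0.5 × √(2(1 − r)). For r = 0.3, 0.5 and 0.7 this is 0.592, 0.500 and 0.387, with totals of 92, 128 and 212. The true effect with no control change is 0.5 for a change-score analysis and 0.5 × √(2/(1 + r)) for ANCOVA. Across both metrics, the three correlations and both models:

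- Lowest power: baseline-SD metric, r = 0.3, total 92, change score (d = 0.5), power 0.660.
- Highest power: baseline-SD metric, r = 0.7, total 212, ANCOVA (d = 0.5 × √(2/1.7) = 0.542), power 0.976.

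So power at the sized total runs from 66% to 98% before any control change enters. This is not the shared-change problem and should not be added to it, but it shows why the metric must be named.

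**Step 4: what the pilot can estimate, and how well.** If all 50 complete, the 95% CI for an SD is 0.84 to 1.25 times the estimate (chi-square, 49 df). For a correlation of 0.5 it is 0.26 to 0.68 (Fisher z, standard error 1/√47). These are usable planning inputs, but wide enough to need a sensitivity range.

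**The case against.** **Aim 4 does not say that the values go in unadjusted.** This is true. A reader might infer that a raw before-after effect will be typed in as a two-arm d. Aim 4 names no metric, test or module, so the documents imply that step at most. What stands is narrower: no between-arm effect can come from these data, and the plan states no conversion or allowance.

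**The direction is not certain.** A reader might also infer that the next trial will be underpowered. The documents do not show that. They give no distribution of symptom duration, and the Purpose section and Aim 2 call the congestion chronic, which argues against much natural resolution. The screening VAS is not among the later instruments, and TNSS is first collected after consent, so some regression may be over before baseline. If controls worsened by 25% of the treated change, power would rise to about 94% in the dz = 0.5 illustration. Shared improvement is plausible; its size is unknown.

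**It is only a pilot.** The later trial is conditional and will need its own sample-size justification, where this could still be corrected. That limits the seriousness. Yet Aim 4 is one of four aims and is the step by which the pilot is meant to inform that trial.

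**Conclusion.** The point holds in this form: Aim 4 bases the size of a randomized trial on uncontrolled effect sizes that do not estimate a between-arm difference, and it states no conversion or allowance for shared change. That conclusion follows from the one-group design and needs no assumed number.

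The cost in power is not known. Under the assumptions above, a trial planned at 80% would have 71%, 56% or 29% if controls showed 10%, 25% or 50% of the change, and would be adequate if they showed none. No share can be read from the documents, and none can be estimated from this study.

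The consequence is confined to planning the later trial. It is no reason to doubt the pilot's description of change in its own participants, and Aims 1 to 3 are unaffected. It should be fixed because the plan, followed as written, can mis-size the next trial and the correction uses the same data.

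**What to change.** Reword Aim 4, for example:

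> Effect sizes will be reported with 95% CIs and the metric named, and labelled as uncontrolled change (PGIC as uncontrolled post-treatment ratings without a baseline). They will not be entered in G-Power as between-arm effects. For TNSS, BPQ and HADS we will estimate the week-5 SD, the baseline-to-week-5 correlation and retention, and for PGIC the week-5 distribution, each with a 95% CI. The future randomized trial will be sized on a justified between-arm difference for its primary outcome against its named comparator, using these estimates and a sensitivity range over their confidence limits.

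This changes the wording of one aim and some summary calculations. It needs no new data, visits or questionnaires. The real cost is that the team must justify a between-arm difference and name a comparator, neither of which the documents now give, and the next trial may turn out larger than uncontrolled effect sizes would suggest.

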The VVC is based on the documented neuroanatomical and neurophysiological pathways between the brainstem areas that regulate the muscles of the face (via special visceral efferent pathways) and the heart and lungs (via the vagus). Features of the VVC may serve as a clinical checklist converging on symptoms of anxiety and depression as observed in several clinical disorders including autism (Bal et al., 2010; Patriquin et al., 2011; Porges et al., 2012; Van Hecke et al., 2009), Fragile-X-Syndrome (Heilman et al., 2011), selective mutism (Heilman et al., 2012), prematurity (Doussard-Roosevelt, et al., 1997), prenatal exposure to opiates and alcohol (Suess et al. 1997), PTSD (Sahar et al., 2001), perpetrators of domestic abuse (Umhau et al., 2002), Borderline Personality Disorder (Austin et al., 2007), behavioral regulation problems (Dale et al., 2011), and abuse and neglect (Dale et al., 2009). However, relating symptoms of anxiety and depression to an illness that impacts the functioning of the VVC (i.e., nasal congestion impacts the functioning of the vagus at the lungs) is a novel aspect of the current study.

Additionally, individuals who already have a compromised VVC due to adverse events (history or current), may also be at risk for the continued cycle of VVC complications (i.e., chronic congestion, anxiety and/or depression).

In summary, the function of the SinuSonic (i.e., reducing nasal congestion while improving vagal regulation of the lungs) align with the theoretical principles of the Polyvagal Theory. Thus, our proposed research will serve to determine whether the SinuSonic will have a significant impact on the reduction and management of physical and psychological symptoms (i.e., anxiety and depression), as they are described within the context of a dysregulated VVC.

Flowchart of Research Procedures:

Participants

50 adults (aged 18-99 years) with self-reported nasal congestion will be recruited for the study. Participants must be US residents.

Data Collection Procedures

Step 1: Recruit/Eligibility Screening

Individuals who make a purchase of the SinuSonic device will receive a recruitment flyer in the shipping box for their device, but only new users of the SinuSonic will be eligible to participate. The recruitment flyer will contain a QR code that users can scan to access the Eligibility Screening for the study in RedCap. Staff at SinuSonic has agreed to include the recruitment flyer when shipping packages.

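### Aim 4 sizes the next trial from effect sizes observed in at most 50 people, with no interval, cautious bound, smallest worthwhile difference or pre-named sizing outcome

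*Combined protocol and SAP*

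**What the plan says.** The last paragraph of the Purpose section makes sizing the next study an object of this one: "data from the study will be used to estimate effect sizes and inform a larger, randomized trial". The same sentence adds the condition "if warranted by the results", with no numeric rule.

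The Participants section sets the number: "50 adults (aged 18-99 years) with self-reported nasal congestion will be recruited for the study". There is one group, and no allowance for dropout is given, so 50 is a ceiling for paired data.

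Aim 4 of Data Analyses then gives the procedure. First: "Calculate effect sizes for each outcome variable, which will be necessary to determine adequate sample size for a future clinical trial". Second: "G-Power software will be used to determine sample sizes based on the effect sizes of the current outcome measures".

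The effects concerned are changes within people over time. For example, Aim 2B says "Repeated measures ANOVA will be used to evaluate mean change in BPQ across time".

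The plan does not use the term point estimate, but it describes nothing else. It states no interval, lower bound, shrinkage, minimal important difference, primary outcome, alpha or power for this step.

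**The concern.** An effect size from 50 people is imprecise, and the required sample size varies with the inverse square of the effect, so modest error in d becomes large error in n. Entering only the observed value in G-Power yields a figure that looks exact and hides that range.

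Two selection routes could also push the planning value upward. One is going ahead only after a favourable result. The other is letting whichever outcome shows the largest effect set the size. The plan prescribes neither in numeric terms, but it guards against neither.

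At stake is a stated deliverable of the study: a next trial planned on this basis could be well short of its intended power. The data and participants of the present study are not affected.

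**Working it through.** The documents give no sample size calculation, so there is no figure to reproduce.

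**Inputs from the documents:** 50 recruited; one group; an effect size for each outcome; observed effects used as planning values.

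**Assumptions, because the documents are silent:** two-sided 5%, 80% power, 1:1 allocation, 50 completers, standardized effects of 0.2 to 0.8, and the paired pre-post d taken as the between-arm d. The last two of these other than the effect range (full completion, and pre-post equal to between-arm) favour the plan.

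**Step 1: interval for d.** With t = d√50 on 49 degrees of freedom, the 95% limits are the values δ for which a noncentral t with noncentrality δ√50 puts 97.5% or 2.5% of its probability below the observed t.

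- d = 0.40: t = 2.83; limits 0.110 and 0.686.
- d = 0.50: t = 3.54; limits 0.203 and 0.792.

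**Step 2: size per arm.** n = 2 × ((1.960 + 0.842)/d)², rounded up.

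| Observed d | n at the estimate | n at the upper limit | n at the lower limit |
|---|---|---|---|
| 0.40 | 2 × (2.802/0.40)² = 98.1, so 99 | 34 | 1,300 |
| 0.50 | 2 × (2.802/0.50)² = 62.8, so 63 | 26 | 380 |

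The range is about 38-fold at 0.40 (1,300/34) and about 15-fold at 0.50 (380/26).

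**Step 3: going ahead only after a significant pilot (assumed rule).** With 50 pairs, significance needs an observed d of at least 2.010/√50 = 0.284. If the true d is 0.3, nearly every pilot that passes overestimates it. In 200,000 simulated pilots per setting, each sized from its own estimate:

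| True d | n needed per arm | Pilots significant | Next trial too small, given significance | Median real power, given significance |
|---|---|---|---|---|
| 0.2 | 393 | 28% | 100% | 35% |
| 0.3 | 175 | 55% | 92% | 58% |
| 0.4 | 99 | 79% | 64% | 72% |
| 0.5 | 63 | 93% | 54% | 78% |
| 0.8 | 25 | 100% | 49% | 81% |

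Without that rule, over all pilots with a positive estimate, 49% to 55% are too small.

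**Step 4: largest of several outcomes (assumed choice).** Four outcomes are measured both at week 0 and at week 5: TNSS, BPQ, HADS anxiety and HADS depression. PGIC has no week-0 value and the SF-12 has no week-5 value. With equal true effects and an assumed correlation of 0.4, sizing on the largest of the four is too small in about 84% to 86% of pilots for true effects from 0.3 to 0.8. At a true d of 0.3 the median planning value is 0.42. That gives 2 × (2.802/0.42)² = 89 per arm where 175 are needed. The real power is then Φ(0.3 × √(89/2) − 1.96) = Φ(0.04), about 52%.

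**Step 5: a cautious bound.** For an observed d of 0.40 the one-sided 80% lower limit is 0.274, so n = 2 × (2.802/0.274)², about 209 per arm against 99. This helps but does not remove selection. By construction the limit exceeds the true value in 20% of all pilots. Among significant pilots that is 20/55 = 36% at a true d of 0.3 and 20/28 = 71% at 0.2.

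**The case against.** The case for the plan is that this is a pilot, and estimating effects is a normal use of one. The future trial is not being designed in this document. Aim 4 refers to sample sizes in the plural, one for each outcome, and nowhere says that the largest effect will govern. If the next trial were powered for every outcome, the smallest effect would govern and the bias would run towards too large a trial. No significance rule is stated for going ahead. The Background reports significant improvement in congestion over five weeks in an earlier study, so a small true effect cannot be presumed for every outcome.

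Much of this stands, and it limits the point. A reader might infer that the future size would be mostly sampling error. The documents do not support that: with 50 people and d near 0.4, sampling error is anywhere from 68% down to 19% of the variance of the estimates, as the assumed SD of true effects rises from 0.10 to 0.30. A reader might also infer that a promising pilot will usually lead to too small a trial. That holds for true effects up to about 0.4 under an assumed significance rule, or if the best outcome is picked. From 0.5 upward, selection on significance alone is close to an even chance, and median power is near its target.

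What the objection does not answer is the width of the interval and its absence from the plan. Both remain at any true effect and under any rule for going ahead. Nor does pilot status excuse them, because sizing the next trial is a numbered aim of this pilot.

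**Conclusion.** The point holds in a limited form. Aim 4 uses observed effects from at most 50 people as planning values and reports nothing about their uncertainty, although the data would be compatible with sizes differing about 15-fold at an observed d of 0.50 and about 38-fold at 0.40. The chance that the next trial is too small depends on a true effect and a rule for going ahead that the documents do not give. After a significant pilot it runs from about 92% (true d 0.3) to about 49% (true d 0.8). Choosing the largest of four outcomes, which the plan neither states nor rules out, would raise it to about 84% to 86%.

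All per-arm figures rest on the assumptions listed above, including full completion and a pre-post effect equal to the between-arm effect. Whether an uncontrolled pre-post change is the right quantity for a randomized trial is a separate problem, and a better interval would not solve it. The change is a cheap improvement to the plan; nothing here invalidates the study.

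**What to change.** Amend Aim 4 as follows.

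1. Report every effect size with its 95% confidence interval.
2. Name, before the data are seen, the one outcome that will set the size of the future trial.
3. Compute that size from this study's SD and within-person correlation together with a justified smallest worthwhile difference. The change among people who rate themselves minimally improved on the week-5 PGIC can support the choice of difference but should not set it alone, because that subgroup of at most 50 people may be small.
4. If an observed effect is used, show the size at a lower confidence limit next to the point-estimate size. For an observed 0.40 that means 209 per arm (one-sided 80% limit, 0.27) beside 99.

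The cost is a change of wording in the analysis section, plus the work of justifying a smallest worthwhile difference; no new data are needed. The downside is that the planned future trial becomes larger.
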